2.6.5 Data Collection

We will ask participants to complete baseline and 6-month surveys online or by telephone interview. In addition, we will make available brief (10 minute) surveys monthly via web, text-message or interactive voice on the primary and select secondary outcomes.

2.6.6 Human Subjects Protection

All procedures will have prior review and approval from the LSU Health Sciences Center-New Orleans (LSUHSC-NO) Institutional Review Board (IRB), and partnering research institutions will enter into reliance agreements with LSUHSC-NO.

2.6.7 Power calculations

The power calculations were based on expecting a percentage point difference between groups ranging from 8 to 10. With enrolling 600 to 720 individuals per group (1200 to 1440 in total), 80% power was projected to detect the difference between groups ranging from 9.3% to 10.7% with alpha level of 0.05 (two-sided) and ICC=.01, allowed a retention rate of 65-75% at 6 months follow-up.²⁷ For outcome measures assessed monthly during the 6-month period, the proposed sample size with 60% retention is adequate for a between group difference of 7.3-7.9%.

2.7 Proposed Analysis

2.7.1 General Issues

a) Modeling. We will use an intent-to-treat (ITT) framework and hierarchical approach with information on programs, service providers/staff, and clients. We will conduct bivariate analyses to identify potential covariates for multiple regressions and compare unadjusted and adjusted intervention coefficients to assess confounding. We will explore transformations and two-part models for skewed counts with smearing estimates for retransformation. b) Missing data. For missing data (item or survey non-response) we will use logical imputation for items as

appropriate and hot-deck multiple imputation using a predictive mean-matching method for item non-response.^{29,30} c) Weights. We will create enrollment weights to represent intended populations.^{31,32} d) Multiple Comparisons. We will consider methods that incorporate bounds on probability of false findings of significance, e.g., false discovery rate.³³ e) Multilevel Data: We will apply multi-level (i.e., hierarchical or random coefficient) models to account for clients within programs and three-levels for longitudinal data having repeated measures within clients.²⁷

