2.3.2 CEP for Coalitions (TA+CEP)

CEP uses a manualized intervention to create multi-sector networks to collaborate in evidence-based and community-prioritized toolkits or intervention materials.^{9,10} The CEP manual used for C-LEARN was developed by adapting pre-existent and study-supported coalition-building intervention materials.^{3-6,11-15} The intervention seeks to catalyze innovative cross-sector solutions devised by participating agencies. CEP supports a series of biweekly to monthly meetings over no more than three months to develop network and individual program capacity, prepare stakeholders as co-leads, and create a written training plan following CPPR principles.^{1,7} CEP councils consider local context, i.e., cultural assets and stakeholder input. Disaster preparedness and public health sectors will be encouraged to offer education/resources on social determinants and disasters within CEP training plans. CEP may be supported by adjunctive resources such as a Learning Collaborative, pending participant interest. The end-goals of CEP are for coalition members a) establish relationships across sectors and b) among the coalition, to create and implement an innovative approach to improve community resilience and capacity.

Participating programs randomized to CEP will also receive the TA materials described in the previous section.

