2.7.6 Mixed-Methods Analyses

For thematic analyses we will enter data into MaxQda software. Academic and community members identify themes coding 5-10 percent together and resolving discrepancies by consensus.^{44,45} We will code data deductively based on study goals, e.g., training plans, and inductively based on emergent themes, e.g., new priorities.⁴³ We will conduct comparative analyses to identify themes across coalitions and triangulate results to describe context, strategies to address resilience, implementation strategies and outcomes. All analyses will be partnered with stakeholders.⁴⁴

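### CEP works through shared coalitions, but no described Aim 2 analysis has a coalition term; if coalitions differ in effect, the CEP–TA interval would be too narrow for a claim about CEP as a strategy

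*Combined protocol and SAP*

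**What the plan says.** Section 2.3.1 describes TA as support for individual programs, delivered by expert webinars. Section 2.3.2 describes CEP as a group process: "CEP supports a series of biweekly to monthly meetings over no more than three months to develop network and individual program capacity". It also has the participants produce a written training plan, and one of its end-goals is, "among the coalition, to create and implement an innovative approach to improve community resilience and capacity".

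On analysis, section 2.7.1 (item e) specifies "multi-level (i.e., hierarchical or random coefficient) models to account for clients within programs", with a third level only for repeated measures within clients. Section 2.7.2 adds two further Aim 2 analyses. The program analysis reports chi-square statistics and controls for service sector and community. The staff analysis of training hours uses two-level hierarchical models whose levels are not named.

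Section 2.6.7 plans with "alpha level of 0.05 (two-sided) and ICC=.01", a single ICC. Coalitions appear only in the qualitative work: case studies in section 2.7.4 and, in section 2.7.6, "comparative analyses to identify themes across coalitions". Their number and size are not given.

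**The concern.** Programs in one CEP coalition share one realisation of the intervention: the same meetings, the same plan, the same joint approach. An unusually strong or weak coalition would shift all its programs in the same direction. The documents describe no such grouping among TA programs. This is clustering created by delivery, in the CEP arm, and it is distinct from the affiliated clusters that section 2.5.1 randomizes as one unit.

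A model that stops at programs counts up to about 30 CEP programs as separate observations of CEP, when there may be only a few coalitions. That matters because Aim 2 asks which capacity-building strategy works better, and section 2.7.7 takes the findings on to policy recommendations. That is a claim about coalitions in general. The secondary program outcomes are also exposed: a partnership between two members of one coalition can count for both.

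**Working it through.** **Inputs from the documents.** Enrolment of 600 to 720 per group, 80% power, two-sided alpha 0.05 and ICC .01 (section 2.6.7), which also "allowed a retention rate of 65-75% at 6 months follow-up"; up to 60 programs (section 2.6.2).

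**Assumptions.** 30 programs per arm; a 50% rate; C equal-sized coalitions with C = 2, 4 or 6; coalition ICC ρ of .002, .005 or .01, added to the program ICC. Two coalitions would be one for each of the two communities in sections 2.6.1 and 2.6.2. At a 50% rate these ρ values mean a between-coalition SD of √(0.25ρ) = 2.2, 3.5 and 5.0 percentage points.

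**Step 1: reproduce the plan's figure.** With n retained clients per arm and m = n/30 per program, the design effect is DE = 1 + (m − 1) × .01 and the variance of the difference is V0 = 2 × 0.25 × DE/n.

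- 600 at 65%: n = 390, m = 13, DE = 1.12, V0 = .001436, SE = 3.79 points. Detectable difference (1.96 + 0.84) × 3.79 = 10.6 points (10.8 with t on 58 df).
- 720 at 75%: n = 540, m = 18, DE = 1.17, V0 = .001083, SE = 3.29 points. Detectable difference 9.2 points (9.4 with t).

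The plan states: "80% power was projected to detect the difference between groups ranging from 9.3% to 10.7" percent. Program clustering alone reproduces this range, so it holds no allowance for coalitions.

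**Step 2: add coalitions in the CEP arm.**

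- True variance: V0 + 0.25ρ/C.
- Variance that a program-only analysis would estimate: V0 + 0.25ρ(1 − 1/C)/29, because some between-coalition spread shows up as spread between programs.
- r = √(true/estimated). Coverage of a nominal 95% interval = 2Φ(1.96/r) − 1, and error = 1 − coverage.

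Example, C = 2 and ρ = .005, 600 at 65%: true variance .001436 + .000625 = .002061; estimated .001436 + .0000216 = .001458; r = √(.002061/.001458) = 1.189; coverage 90.1%; error 9.9%.

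Each pair below runs from 600 at 65% to 720 at 75%.

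| C | ρ | r | Coverage (%) | Error (%) |
|---|---|---|---|---|
| 2 | .002 | 1.080–1.105 | 93.0–92.4 | 7.0–7.6 |
| 2 | .005 | 1.189–1.243 | 90.1–88.5 | 9.9–11.5 |
| 2 | .01 | 1.348–1.439 | 85.4–82.7 | 14.6–17.3 |
| 4 | .002 | 1.038–1.050 | 94.1–93.8 | 5.9–6.2 |
| 4 | .005 | 1.091–1.119 | 92.8–92.0 | 7.2–8.0 |
| 4 | .01 | 1.172–1.220 | 90.6–89.2 | 9.4–10.8 |
| 6 | .002 | 1.024–1.031 | 94.4–94.3 | 5.6–5.7 |
| 6 | .005 | 1.057–1.074 | 93.6–93.2 | 6.4–6.8 |
| 6 | .01 | 1.108–1.140 | 92.3–91.5 | 7.7–8.5 |

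With ρ = 0, r = 1 and nothing changes. The factor 0.25 cancels in r, so the 50% rate affects the differences in points but not the coverage or error.

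**Step 3: check by simulation.** A program-level t-test (58 df), with coalition effects drawn around a mean of zero, rejects in about 7–8%, 10–11% and 14–17% of runs at ρ = .002, .005 and .01 with two coalitions, and in about 6–8.5% with six. This agrees with the table.

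**Step 4: power.** With two coalitions and ρ = .005, the difference detectable with 80% power, judged by the true SE, becomes 2.80 × √.002061 = 12.7 points (600 at 65%) or 11.6 points (720 at 75%). Power at the differences from Step 1 falls to 65% and 61%. With a single coalition, its effect cannot be separated from that of CEP.

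**The case against.** A reader might infer that the planned interval is simply wrong, or that every Aim 2 model treats CEP programs as independent. The documents support neither.

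- The shortfall exists only if coalition variance is above zero and the target is CEP beyond the coalitions formed. Treating coalitions as fixed is a legitimate choice, and a test of no effect on anyone stands. This limits the point; it does not remove it, since Aim 2 is worded as a comparison of strategies and no text restricts the conclusion.
- The levels of the staff model are unnamed, and section 2.7.1 allows random coefficient models in general terms. So the plan leaves coalitions out rather than committing to independence. Even so, no coalition term is described anywhere.
- The program analysis controls for community. That is stated only for this secondary analysis, and a community term is shared by both arms, whereas coalition variation arises only under CEP.
- The size may be trivial. Section 2.5.1 calls all interventions encouragement interventions, CEP meetings last at most three months, and the top of the assumed range (.01) equals the whole planning ICC. This stands: the documents cannot fix the size.
- TA webinars might also be attended jointly. That is possible, but the documents describe no TA groups that plan or act together, and CEP programs receive the TA materials as well.

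**Conclusion.** The concern holds in conditional form. The plan builds joint action into one arm and provides no analysis for it. If coalitions differ, the CEP–TA interval would overstate precision for CEP as a strategy.

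Over the assumed range the consequence runs from slight (error about 6% with six coalitions and ρ = .002) to serious (about 17% with two coalitions and ρ = .01). It is nil if coalition variance is zero. The number of coalitions, the coalition ICC and 30 programs per arm are all assumptions, the last being the ceiling implied by up to 60 programs. No single figure from the table should be read as the trial's actual error rate.

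**What to change.** 1. Record the coalition of each CEP program, and state in the SAP how many coalitions there are and how large they are. The case studies in section 2.7.4 already draw on meeting notes and written plans, so this should need little extra work.
2. If there are enough coalitions, add a coalition random effect in the CEP arm only (a partially nested model) with small-sample degrees of freedom. Set the required number before outcome data are seen.
3. If there are few, do not fit that term: one coalition gives no information on coalition variance and two give almost none. Instead, state the Aim 2 result as the effect of the coalitions formed in this study, show each coalition against the TA programs of its own community, and report a sensitivity interval over assumed coalition ICCs, for example 0 to .01.
4. Do the same for the staff and program analyses, and name the levels of the staff model.

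The cost is SAP text and one sensitivity table, with no change to design or randomization. The price is a wider interval and, with few coalitions, a conclusion confined to those studied.

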2.5 Randomization

2.5.1 Program-level (CEP vs TA)

Within each community, programs will be matched based on a) range of services offered, b) clientele base (i.e. people with serious mental illness, formerly incarcerated people, etc.), c) program size, and d) existing partnerships or affiliations. “Affiliation” refers to having a strong referral relationship and/or clients within and across programs. Programs that match on multiple categories or identify that they are part of an existing partnership or affiliation will be paired. Matched pairs will fall within four different types of grouping:

- 1) Unique Program: There is no similar program to match with. Will be randomized independently.
- 2) Paired Program: Two programs that are similar in the criteria described above are paired and do not have affiliations with other programs in the study. One program is randomly assigned to one of the interventions. The other program will be assigned to the other intervention.

- 3) Unique Cluster: Programs that are affiliated with more than one other program. All programs in the cluster will be treated and randomized as one unit.
- 4) Cluster Pair: Two sets of clustered programs that are reasonably similar as a whole to each other. One cluster will be randomized to one of the interventions. The other cluster will be assigned to the other intervention.

By pairing programs following this schema, we reduce the chance of intervention contamination; that is, an individual client may receive services from multiple programs enrolled in the study. Community Investigators in the C-LEARN Leadership Council will review matching to ensure that programs are appropriately paired.

After matching, we will then randomize programs or program clusters using a random seed to TA or TA+CEP.^{24,27} All interventions are “encouragement” interventions. That is, participants are encouraged to consider interventions to which they are assigned, no one is forced to follow a given protocol. This is more of a public health rather than a clinical approach to intervention implementation.

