2.6.2 Programs

We will select eligible programs by combining program lists with community nominations, classifying programs as mental health, substance abuse, primary care/FQHCs/public health (health) or social services, community centers, parks and recreation community centers, businesses, salons, gyms, faith-based, and disaster preparedness/response programs (community).²⁸ We will invite programs through letters, phone calls and visits to recruit as many as 30 per community, expecting as many as 60 total programs.

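### Whole clusters of affiliated programs are randomised, some units in matched pairs, but the CEP vs TA models stop at the program, so standard errors can be wrong in either direction

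*Combined protocol and SAP*

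**What the plan says.** Section 2.5.1 defines four kinds of unit: unique programs, paired programs, unique clusters and cluster pairs. After matching, "we will then randomize programs or program clusters using a random seed to TA or TA+CEP". A unique cluster consists of "Programs that are affiliated with more than one other program", so at least three programs share one allocation: "All programs in the cluster will be treated and randomized as one unit". A cluster pair is "Two sets of clustered programs that are reasonably similar as a whole to each other", with one cluster going to each arm. Paired single programs are split between arms in the same way. Affiliation means "having a strong referral relationship and/or clients within and across programs".

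The analysis sections describe a different structure:

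- Section 2.7.1(a) lists programs, staff and clients as the sources of information for the hierarchical approach.
- Section 2.7.1(e) specifies "models to account for clients within programs and three-levels for longitudinal data having repeated measures within clients".
- Section 2.7.2 uses two-level models for staff training hours without naming the levels. Program outcomes are adjusted for sector and community.
- Section 2.7.3 adds only the two intervention indicators and their interaction.

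None of these gives a random effect for the randomised cluster, a variance robust at that unit, a pair term, or degrees of freedom based on randomised units. Section 2.6.7 uses a single ICC of .01, does not say at which level it applies, and mentions neither clusters nor matching.

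**The concern.** The analysis should follow the allocation. Where three or more programs receive one arm from one draw, anything those programs have in common is confounded with that draw. A program random effect treats them as separate pieces of evidence. The protocol itself makes correlation plausible, because it groups programs for their referral ties and shared clients.

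Matching works the other way. If paired units resemble each other, the difference between arms varies less than an unmatched model assumes, so leaving out the pair makes the interval too wide and costs power.

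At stake is CEP vs TA on both primary client outcomes, MCS-12 and PHQ-8. For unique and paired single programs the program is the randomised unit, so there the modelled level is right and only the pair term is missing.

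**Working it through.** **Inputs from the protocol.** "expecting as many as 60 total programs" (2.6.2). In 2.6.7: 600 to 720 enrolled per group, retention 65-75%, and "80% power was projected to detect the difference between groups ranging from 9.3% to 10.7% with alpha level of 0.05 (two-sided) and ICC=.01". Analysed per group: 600 × 0.65 = 390 to 720 × 0.75 = 540.

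**Assumptions not in the protocol.** Equal program sizes, 30 programs per arm, outcome proportion .5, cluster sizes, and the share *s* of the ICC that is common to programs in one cluster.

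**1. Reproduce the stated detectable difference.** With *m* retained clients per program and *k* programs per cluster:

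DE = 1 + (m − 1)(.01) + (k − 1)·m·(.01)·s; detectable difference = 2.80 × √(2 × .25 × DE / n)

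With independent programs (k = 1):
- n = 390, m = 13: DE = 1.12, difference 10.6 points (stated 10.7).
- n = 540, m = 18: DE = 1.17, difference 9.2 points (stated 9.3).

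The stated range is thus consistent with clustering at program level only.

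**2. Put every program in a cluster of 3.**

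| n per arm | s | DE | Detectable difference | Program-only SE ÷ true SE |
|---|---|---|---|---|
| 390 | 50% | 1.12 + .13 = 1.25 | 11.2 | √(1.12/1.25) = .95 |
| 390 | 100% | 1.12 + .26 = 1.38 | 11.8 | √(1.12/1.38) = .90 |
| 540 | 50% | 1.17 + .18 = 1.35 | 9.9 | √(1.17/1.35) = .93 |
| 540 | 100% | 1.17 + .36 = 1.53 | 10.5 | √(1.17/1.53) = .87 |

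These use the normal multiplier 2.80. Degrees of freedom based on fewer units would raise the differences further.

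**3. Type I error, unpaired units.** Data were simulated under no effect, 40,000 replicates per setting (Monte Carlo SE about 0.1 point), with 60 programs of 15 clients. Between-program variance totals .01 and the error variance of a program mean is .99/15. The test is a t test on program means with 58 df, standing in for a balanced random-intercept model.

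| Mix of units | s = 25% | s = 50% | s = 100% |
|---|---|---|---|
| 24 singles + 12 clusters of 3 | 5.4% | 5.9% | 7.1% |
| 30 singles + 6 clusters of 5 | 5.8% | 6.6% | 8.1% |
| 20 clusters of 3 | 5.7% | 6.6% | 8.2% |

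- Control with 60 independent programs: 4.8-5.1%.
- Between-program variance floored at zero, as in a mixed model: 5.0-5.3%, 5.4-6.2% and 6.6-7.7% for the three shares.
- Only 4 clusters of 3 among 48 singles: 5.0-5.6%.

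Hand check for 20 clusters of 3 at s = 100%: DE rises from 1.14 to 1.14 + 2 × 15 × .01 = 1.44. The SE ratio is √(1.14/1.44) = .89, and the two-sided tail beyond 1.96 × .89 = 1.74 is about 8.1%, in line with the simulated 8.2%.

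**4. Type I error, every unit paired, pair ignored.** Ranges are over the same three mixes.

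| Share of ICC carried by the pair | Rest split equally between unit and program | Rest all at unit level |
|---|---|---|
| 50% | 4.6-5.0% | 5.2-6.0% |
| 75% | 4.2-4.4% | 4.4-4.9% |

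With single programs in pairs, 18 clients each, and the pair explaining 50-80% of program variance, the rate is 4.2-3.7%.

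**The case against.** The strongest reply is that the effect may be negligible. Section 2.5.1 intends similar programs to be paired, so a trial made up only of unmatched clusters is unlikely, and with every unit paired the error rate lies on either side of 5%. With few clusters, or with a mixed-model variance floor and a modest cluster share, it stays near nominal. Recruitment was interrupted by COVID-19. With 8 clients per program (an assumption), the floored test gives 4.5-5.3% for 24 singles plus 12 clusters of 3, and 4.9-6.0% when all programs are in clusters of 3. All of this stands as a limit on size. It does not remove the mismatch, and the protocol gives no counts that would rule out the less favourable mixes.

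Second, treating a cluster as one unit might mean that it counts as one program in the analysis. Sections 2.7.1 to 2.7.3 do not say so, and 2.7.1(e) names programs. For staff the objection has more force: the upper level of the two-level model is not named. What can be said there is that the randomised unit is not specified; no error rate is claimed for staff or program outcomes.

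Third, the power match proves little. With proportion .40 and 20 units per arm, the same formula gives 10.7 (n = 390, DE 1.185) and 9.4 (n = 540, DE 1.26), an equally close fit. That is correct, so step 1 is an illustration and not evidence that clusters were ignored in the power calculation.

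Fourth, omitting the pair costs power and not validity, and a pair term uses degrees of freedom. That is also fair, but the interval would still not reflect the design.

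**Conclusion.** The concern holds and should be fixed. Followed as written, the CEP vs TA client model treats programs allocated together as independent and ignores matching.

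The omission can be read directly from the text; its size cannot. At an ICC of .01 the distortion is modest: up to about 8% type I error in the worst unpaired case examined, where the whole ICC is shared within a cluster, and slightly below 5% where strong matching is ignored. Larger clusters would do more harm: with all programs in unpaired clusters of 5 and 18 clients each, the simulated rate is 8.9-13.0% for shares of 50-100%. If no clusters or pairs were formed, the problem disappears.

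If all programs were in clusters of 3 and matching gave no gain, the detectable difference would move from 9.2-10.6 points to 9.9-11.2 (half the ICC shared) or 10.5-11.8 (all of it). Section 2.6.7 expects a difference of only 8 to 10 points.

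**What to change.** In 2.7.1(e) and 2.7.2, state that in every CEP vs TA analysis:

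- the top level is the randomised unit (single program or program cluster) with programs nested in it, or the variance is robust at that unit;
- degrees of freedom are based on the number of randomised units;
- the matched pair is included where units were paired;
- the same rule applies to program and staff outcomes, for which a permutation test that follows the actual allocation is one option.

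In 2.6.7, restate the detectable difference by number and size of randomised units, with the assumed split of the ICC between cluster and program. Report how many single programs, program pairs, clusters and cluster pairs were randomised.

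The cost is wording and one more model level, with no new data. Degrees of freedom fall, for example from 60 − 2 = 58 to 20 − 2 = 18 if all programs were in clusters of 3. The CEP vs TA interval may then widen somewhat, though the pair term may recover part of that.
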